6.2.2.1. Evaluation for Gastrointestinal Events/Colitis

For Grade 2 colitis and diarrhea (unless clinical diagnosis is established from medical history and physical examination), the following testing is required:

- Stool culture for routine pathogens (Salmonella, Shigella, Campylobacter species, Clostridium difficile toxin, Rotavirus, Cytomegalovirus, Adenovirus)
- Stool for Ova and Parasites (Cryptosporidium parvum, Isospora belli, Enterocytozoon bieneusi, Septata intestinalis, Strongyloides, Microsporidia, Entamoeba histolytica, Cyclospora), Giardia antigen

For Grade ≥ 3 or persistent Grade 2 colitis or diarrhea without clear etiology (eg, clostridium difficile enterocolitis), endoscopy with biopsy is strongly recommended. All biopsy samples should include immunohistochemistry (IHC) and PCR for CMV, Adenovirus.

PPD

6.2.2.2. Differentiation Between Small-bowel and Large-bowel Diarrhea

Differentiation between small-bowel and large-bowel diarrhea on a clinical basis if recommended. If unclear, consider upper and lower tract endoscopy with biopsy.

- Small bowel diarrhea is characterized by large volume diarrhea (more than one per day), possibly associated dehydration weight loss and paraumbilical pain. Consider an endoscopic small-bowel biopsy and evaluate other etiologies such as celiac disease.
- Large-bowel diarrhea may present with lower pelvic pain, tenesmus, generally smaller stool volumes with gross blood frequently found in the stool. Consider a colonoscopic evaluation and biopsy.

6.3. End of Study

Subjects will be withdrawn from this study if they develop progressive disease, unacceptable toxicity related to idelalisib, withdraw consent, are noncompliant, or are lost to follow up or die. In this event, the following procedures should be performed:

- Return of used and unused drug supply
- Recording of all Grade AEs and all SAEs
- Investigator Response Assessment
- Laboratory assessments as outlined in [Table 6-1](#)
- Recording of the reason for withdrawal
- Deaths occurring within 30 days following the last dose of idelalisib, even if occurring after the End of Study Visit, will be captured.

Table 6-1. Schedule of Study Procedures

Period	Screen	Treatment														End of study	
Visit	1	2	3	4	5	6	7	8	9	10	11	12	13	14	15+		End of study
Week	-4	0	2	4	6	8	10	12	14	16	18	20	22	24	Q4 weeks	Q12 weeks	End of study
Study Day	Within -28 days	1	14	28	42	52	70	84	98	112	126	140	154	168			End of study
Visit Window			±2	±2	±2	±2	±2	±2	±2	±2	±2	±2	±2	±2	±7	±7	
Informed consent	X																
Serum β-HCG ^a	X																
Pneumococcal, Hib, Tetanus titers	X																
ALT/AST/total bilirubin	X	X		X		X		X		X				X		X	
Urine pregnancy test ^a		X		X		X		X		X				X		X	
ANC ^b	X	X	X	X	X	X	X	X	X	X	X	X	X				
CMV surveillance	X			X		X		X		X		X		X	X ^c		
Immune Monitoring	X			X				X						X		X	
Assess adverse events and SAEs ^d		X		X		X		X		X				X		X	
Record concomitant medications ^e		X		X		X		X		X				X		X	
Idelalisib dispensing/accounting		X		X		X		X		X				X		X	
Investigator response assessment ^f	X			X		X		X		X				X		X	

Abbreviations: β-HCG=beta human chorionic gonadotropin, ALT=alanine aminotransferase, AST=aspartate aminotransferase, Hib = Haemophilus Influenzae Type B

a For women of child bearing potential; Serum β-HCG to be collected at screening, urine pregnancy test to be collected at visits from first dose of idelalisib to EOS

b Absolute neutrophil count (ANC) will be monitored at least every two weeks for the first 24 weeks of idelalisib treatment

c CMV surveillance must be conducted approximately every 4 weeks throughout the course of idelalisib treatment

d For an AE of Diarrhea/Colitis: 1) Obtain history of onset and duration of diarrhea, including description of number of stools and stool composition, travel history, dietary changes and a medication review to identify possible diarrheogenic agents and 2) Perform physical examination including assessment for fever, dizziness, abdominal pain/cramping, and weakness

e Concomitant medications only collected if it is related to an AE

f Record investigator response assessment if obtained per standard of care

7. ADVERSE EVENTS AND TOXICITY MANAGEMENT

7.1. Definitions of Adverse Events, Adverse Reactions, and Serious Adverse Events

7.1.1. Adverse Events

An adverse event (AE) is any untoward medical occurrence in a clinical study subject administered a medicinal product, which does not necessarily have a causal relationship with the treatment. An AE can therefore be any unfavorable and/or unintended sign, symptom, or disease temporally associated with the use of a medicinal product, whether or not considered related to the medicinal product. AEs may also include pre- or post-treatment complications that occur as a result of protocol specified procedures, lack of efficacy, overdose, drug abuse/misuse reports, or occupational exposure. Preexisting events that increase in severity or change in nature during or as a consequence of participation in the clinical study will also be considered AEs.

An AE does not include the following:

- Lymphocytosis
- Laboratory abnormalities not requiring clinical intervention or further investigation. Such abnormalities will be captured as part of overall laboratory monitoring.
- Medical or surgical procedures such as surgery, endoscopy, tooth extraction, and transfusion. The condition that led to the procedure may be an adverse event and must be reported.
- Pre-existing diseases, conditions, or laboratory abnormalities present or detected before the screening visit that do not worsen
- Situations where an untoward medical occurrence has not occurred (eg, hospitalization for elective surgery, social and/or convenience admissions)
- Overdose without clinical sequelae
- Any medical condition or clinically significant laboratory abnormality with an onset date before the consent form is signed and not related to a protocol-associated procedure is not an AE. It is considered to be pre-existing and should be documented on the medical history CRF.

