#### **7.1.5. Treatment-Emergent Adverse Events**

##### **7.1.5.1. Definition of Treatment-Emergent Adverse Events**

Treatment-emergent adverse events (TEAEs) are defined as 1 or both of the following:

- Any AEs with an onset date on or after the study drug start date and no later than 30 days after permanent discontinuation of study drug
- Any AEs leading to premature discontinuation of study drug.

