#### 7.1.5.2. Incomplete Dates

If the onset date of the AE is incomplete and the AE stop date is not prior to the first dosing date of study drug, then the month and year (or year alone if month is not recorded) of onset determine whether an AE is treatment emergent. The event is considered treatment emergent if both of the following 2 criteria are met:

- The AE onset is the same as or after the month and year (or year) of the first dosing date of study drug, and
- The AE onset date is the same as or before the month and year (or year) of the date corresponding to 30 days after the date of the last dose of study drug

An AE with completely missing onset and stop dates, or with the onset date missing and a stop date later than the first dosing date of study drug, will be considered to be treatment emergent. In addition, an AE with the onset date missing and incomplete stop date with the same or later month and year (or year alone if month is not recorded) as the first dosing date of study drug will be considered treatment emergent.

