##### 7.2.1.1. Treatment-Emergent Laboratory Abnormalities

Treatment-emergent laboratory abnormalities are defined as values that increase at least 1 toxicity grade from baseline at any postbaseline time point, up to and including the date of last dose of study drug plus 30 days for subjects who permanently discontinued study drug. If the relevant baseline laboratory value is missing, any abnormality of at least Grade 1 observed within the time frame specified above will be considered treatment emergent.

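### Protocol 7.1.1 gives two answers on whether worsening of a condition that began before consent is an adverse event, so a carried-over toxicity that worsens on idelalisib may go unrecorded

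*Protocol*

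**What the plan says.** Protocol 7.1.1 addresses pre-existing conditions in three places.

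- On conditions already present, the opening paragraph says that any which "increase in severity or change in nature during or as a consequence of participation in the clinical study will also be considered AEs".
- The fourth item in the list of what an AE does not include covers prior illnesses and "laboratory abnormalities present or detected before the screening visit that do not worsen".
- The last item in that list says that a medical condition, or a laboratory abnormality of clinical significance, "with an onset date before the consent form is signed and not related to a protocol-associated procedure is not an AE". It adds: "It is considered to be pre-existing and should be documented on the medical history CRF".

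The documents differ on medical history. Protocol 6.1.3 sends exacerbations seen during screening to the medical history form. Protocol 6.2 also classes them as medical history but says that this is not collected. SAP 5.2 says medical history is collected at screening and listed without coding.

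SAP 7.1.5.1 classes an AE as treatment-emergent by date, "Any AEs with an onset date on or after the study drug start date" and up to 30 days after permanent discontinuation, or because it led to premature discontinuation. It has no limb for worsening. For laboratory data, SAP 7.2.1.1 does count worsening: "values that increase at least 1 toxicity grade from baseline at any postbaseline time point". SAP 7.1.6 lists all AEs in the Safety Analysis Set, whether treatment-emergent or not.

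**The concern.** A site has to decide what to do when a toxicity that began on GS-9820 gets worse on idelalisib. Two statements in 7.1.1 lead to an AE record. The third, read literally, leads to the medical history form or, if protocol 6.2 is followed, possibly to no form at all.

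The design makes this more than a drafting matter. Every subject comes from a PI3Kδ inhibitor that protocol 1.3 describes as having a safety profile similar to that of idelalisib. Exclusion criterion 2 bars only toxicities that would preclude starting idelalisib, so lesser ongoing toxicities can be carried in. Grade 3 or higher AEs are a named safety endpoint in protocol 8.2. The study tests no hypothesis and the SAP plans listings, so the safety findings rest on events being captured at the site.

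**Working it through.** The plan states no figure on this point. The check applies the written rules to one test case: a non-laboratory condition, not serious, Grade 1 before consent and Grade 3 on idelalisib.

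**Inputs.** The three statements in protocol 7.1.1; the two limbs of SAP 7.1.5.1; the listing rule in SAP 7.1.6; 3 subjects enrolled (SAP 1.3); approximately 6 planned (protocol 4.1). Neither document says whether a worsened condition keeps its original onset date or receives a new record, so both options are shown.

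| How the event is handled | AE under opening paragraph | AE under last exclusion | Treatment-emergent if recorded | In AE listing |
|---|---|---|---|---|
| (a) Original onset kept, drug not stopped | Yes | No | No | Yes, if recorded |
| (b) Original onset kept, leads to discontinuation | Yes | No | Yes, second limb | Yes, if recorded |
| (c) New record dated at the worsening | Yes | Yes, onset is after consent | Yes, first limb | Yes, if recorded |

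**Where an event can be lost.** The event is missing from the listing only if the site follows the last exclusion and enters no AE. This happens at recording. No step in the SAP drops an AE that has been recorded.

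**What the onset convention settles.** If 7.1.1 required (c), the conflict would disappear. A worsening after first dose would then be treatment-emergent under SAP 7.1.5.1 as written.

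**End of the window.** SAP 7.1.5.1 counts 30 days from permanent discontinuation, while SAP 7.1.5.2 uses "30 days after the date of the last dose of study drug". Permanent discontinuation cannot come before the last dose, so (discontinuation + 30 days) ≥ (last dose + 30 days). The 7.1.5.1 wording can only widen the window, so it cannot exclude an event.

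**Size.** If one affected subject, with no other Grade 3 or higher AE, is missed, the incidence shifts by 1/n:

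- n = 3: 1/3 = 33.3 percentage points
- n = 6: 1/6 = 16.7 percentage points

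Protocol 8.2 and 8.4 speak of incidence and percentages, but the SAP's AE output is a by-subject listing. In that output the effect would be a missing entry.

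**The case against.** The strongest reply is that 7.1.1 can be read consistently. The last exclusion does not mention worsening. It only labels the condition pre-existing, and the opening paragraph then says what happens when a pre-existing event worsens. Two statements count worsening and one is silent. This reading is reasonable, but the text does not state it. The fourth item carries the qualifier and the last does not, which invites a site to treat them differently. Protocol 6.1.3 and 6.2 point the other way by treating exacerbations during screening, after consent, as medical history.

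A second reply is that much is already covered:

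- Serious worsening has its own reporting route under protocol 7.4.
- Laboratory abnormalities that need intervention or change idelalisib dosing must be recorded as AEs under protocol 7.1.3, and SAP 7.2.1.1 counts grade increases.
- AEs leading to discontinuation are treatment-emergent whatever their onset date.
- Exclusion criterion 2 keeps out the toxicities that would preclude idelalisib.

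This stands, and it narrows the point to non-serious, non-laboratory worsening. That group still includes Grade 3 events, because protocol 7.2.2 notes that a severe event need not be serious.

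A reader might also infer that the missing worsening limb in SAP 7.1.5.1 removes such events from the safety data. The documents do not support this. SAP 7.1.6 lists every AE, and no planned AE output is restricted to treatment-emergent events. The most that is lost is the classification, and only if the original onset date is kept.

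**Conclusion.** The inconsistency in protocol 7.1.1 is real and should be corrected. The consequence is conditional: a non-serious, non-laboratory toxicity open at consent that worsens on idelalisib may not be recorded as an AE if the site follows the last exclusion. The fallback to medical history is uncertain because the documents disagree on whether it is collected.

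The 33.3-point shift assumes that one of the 3 subjects had such a toxicity, that it reached Grade 3, that it was left off the AE form, and that the subject had no other Grade 3 or higher AE. Nothing in the documents shows that any enrolled subject was in this position.

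A reader might try to size the problem from the diarrhea and colitis timings in protocol 7.3.2.1. They do not measure it. The onset medians do not show low-grade events progressing to severe ones, and the resolution times are not the length of a hold that ends in a permanent stop.

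**What to change.** **Protocol 7.1.1, last exclusion.** Add an exception: unless the condition becomes more severe or changes in character after consent, in which case the worsening is recorded as a new AE with onset on the date of worsening. Put the same convention in the eCRF completion guideline.

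**Medical history.** Reconcile protocol 6.1.3, 6.2 and 7.1.1 with SAP 5.2, so that one statement says whether it is collected and on which form.

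**Data already collected.** If the database is still open, ask the sites whether any condition present at consent worsened on idelalisib without an AE record.

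**Optional SAP edits.** Add a worsening limb to SAP 7.1.5.1, and end the window there at last dose plus 30 days, to agree with SAP 7.1.5.2 and 7.2.1.1 and protocol 7.4. These edits affect classification only.

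The cost is one clause, a reconciliation of a few sentences and, at most, a site query covering 3 subjects. The downside is a few more AE records.

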7.1.2. Serious Adverse Events

A **serious adverse event** (SAE) is defined as an event that, at any dose, results in the following:

- Death
- Life-threatening (Note: The term “life-threatening” in the definition of “serious” refers to an event in which the subject was at risk of death at the time of the event; it does not refer to an event that hypothetically might have caused death if it were more severe.)

- In-patient hospitalization or prolongation of existing hospitalization
- Persistent or significant disability/incapacity
- A congenital anomaly/birth defect
- A medically important event or reaction: such events may not be immediately life-threatening or result in death or hospitalization but may jeopardize the subject or may require intervention to prevent one of the other outcomes constituting SAEs. Medical and scientific judgment must be exercised to determine whether such an event is a reportable under expedited reporting rules. Examples of medically important events include intensive treatment in an emergency room or at home for allergic bronchospasm; blood dyscrasias or convulsions that do not result in hospitalization; and development of drug dependency or drug abuse. For the avoidance of doubt, infections resulting from contaminated medicinal product will be considered a medically important event and subject to expedited reporting requirements.

7.1.3. Clinical Laboratory Abnormalities and Other Abnormal Assessments as Adverse Events or Serious Adverse Events

Laboratory abnormalities without clinical significance are not recorded as AEs or SAEs. However, laboratory abnormalities (eg, clinical chemistry, hematology, and urinalysis) that require medical or surgical intervention or lead to idelalisib interruption, modification, or discontinuation must be recorded as an AE, as well as an SAE, if applicable. In addition, laboratory or other abnormal assessments (eg, electrocardiogram, x-rays, vital signs) that are associated with signs and/or symptoms must be recorded as an AE or SAE if they meet the definition of an AE or SAE as described in Sections 7.1.1 and 7.1.2. If the laboratory abnormality is part of a syndrome, record the syndrome or diagnosis (eg, anemia), not the laboratory result (ie, decreased hemoglobin).

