5.2.10. Idelalisib Dose Adjustments

The dose adjustment recommendations and requirements in [Table 5-2](#) are based on the Common Terminology Criteria for Adverse Events (CTCAE) grade of specific toxicities. However, exceptions are expected for subjects who initiate study treatment with low blood counts. Clinical judgment should apply, and in cases of uncertainty, the study medical monitor should be contacted.

The dose modification instructions in [Table 5-2](#) focus on the types of events most commonly associated with idelalisib. The modifications include both recommended and required actions. When a modification is indicated as a recommendation, it serves as a guideline; variations from the recommendation may be warranted based on an investigator's individual judgment in considering potential risks, benefits, and therapeutic alternatives available to each subject.

Table 5-2. Dose Adjustment Guidelines {Gilead Sciences Inc 2014}

NCI CTCAE Grade ^a	Idelalisib
HEMATOLOGICAL ADVERSE EVENTS	
Neutropenia	
Grade \leq 2 neutropenia	Recommended Action: Maintain current dose level and schedule.
Grade \leq 3 neutropenia	Required Action: Monitor blood counts at least weekly until ANC \leq Grade 2. Recommended Action: Maintain current dose level and schedule.
Grade 4 neutropenia (or occurrence of neutropenic fever or infection)	Required Action: 
Withhold idelalisib.Monitor blood counts at least weekly until ANC \leq Grade 2 Recommended Action: 
May resume idelalisib at lower dose level when ANC grade is \leq Grade 3Neutropenia should be managed according to established clinical guidelines.
Thrombocytopenia	
Grade \leq 3	Recommended Action: Maintain current dose level and schedule.
Grade 4	Required Action: Withhold idelalisib for bruising or bleeding until Grade \leq 3. Recommended Action: May resume idelalisib at initial or reduced dose level at investigator discretion.
NON-HEMATOLOGICAL ADVERSE EVENT	
Rash	
Grade \leq 1	Recommended Action: Maintain current dose level and schedule
Grade 2	Recommended Action: Maintain current dose level and schedule
Grade \geq 3	Required Action: Withhold idelalisib until Grade \leq 1. Recommended Action: Resume at lower dose level or discontinue idelalisib at investigator discretion.
Stevens-Johnson Syndrome (SJS)/Toxic Epidermal Necrolysis (TEN)	

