8.2. Safety Endpoints

Safety will be assessed with endpoints including incidence of \geq Grade 3 AEs, SAEs, and deaths.

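### Protocol Sections 7.1.1 and 7.1.3 use different tests for when a laboratory abnormality is an AE, so asymptomatic Grade 3 neutropenia on a maintained dose can be recorded inconsistently

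*Protocol*

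**What the plan says.** Protocol Section 7.1.1 lists what is not an AE. One entry is "Laboratory abnormalities not requiring clinical intervention or further investigation", and of these it says: "Such abnormalities will be captured as part of overall laboratory monitoring".

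Section 7.1.3, which deals specifically with laboratory findings, opens with a different exemption: "Laboratory abnormalities without clinical significance are not recorded as AEs or SAEs". It then says that laboratory abnormalities, hematology included, "that require medical or surgical intervention or lead to idelalisib interruption, modification, or discontinuation must be recorded as an AE". A further clause covers laboratory or other abnormal assessments "that are associated with signs and/or symptoms must be recorded as an AE or SAE if they meet the definition" in Sections 7.1.1 and 7.1.2. Neither 7.1.1 nor 7.1.3 uses CTCAE grade as a trigger.

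In Table 5-2 (Section 5.2.10), the neutropenia row that applies at Grade 3 carries "Required Action: Monitor blood counts at least weekly until ANC" is back to Grade 2 or lower. The row ends "Grade 2. Recommended Action: Maintain current dose level and schedule". Section 7.3.4 repeats the weekly requirement for Grade 3 neutropenia.

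On the endpoint, Section 8.2 says: "Safety will be assessed with endpoints including incidence of" Grade ≥3 AEs, SAEs and deaths. The synopsis says the same. SAP Section 7.1.6 provides a listing of all AEs. SAP Section 7.2 provides a laboratory listing for serum chemistry, and SAP Section 7.2.2 a listing of subjects who cross liver-test thresholds.

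**The concern.** The endpoint counts Grade ≥3 AEs, not Grade ≥3 laboratory values. A laboratory toxicity reaches it only if the site records it as an AE, and the two sections that govern that decision use different criteria. Further investigation appears only in 7.1.1. Dose change appears only in 7.1.3. Clinical significance, the basis for not recording in 7.1.3, is not defined.

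A gap like this matters most where the protocol's own management of an expected toxicity consists of extra testing without treatment or dose change, and Grade 3 neutropenia is that case. Two sites that both follow the protocol could handle the same event differently, and whether it counts would depend on which section was consulted rather than on its grade. In a study with 3 enrolled subjects, every event is a visible part of the safety record.

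**Working it through.** The plan states no figure to reproduce: there is no hypothesis test, and SAP Section 1.3 gives no sample size calculation. The check is a comparison of the rules, followed by a small calculation for scale.

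**Step 1. Is weekly testing additional?** Section 6.2.2 schedules ANC every 2 weeks through Week 24. Weekly counts at least double that rate: over 4 weeks, at least 4 counts instead of 2. The extra counts are triggered by the abnormality, so calling them further investigation is a natural reading, though not the only one.

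**Step 2. Is there an intervention on the default path?** Section 5.3.5 allows G-CSF for Grade 4 neutropenia or neutropenic complications. Uncomplicated Grade 3 neutropenia on the recommended path therefore brings neither treatment nor dose change.

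**Step 3. Apply both sections.**

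| Event and management | Section 7.1.1 | Section 7.1.3 | Shown in the SAP without an AE record? |
|---|---|---|---|
| Grade 3 neutropenia, asymptomatic, dose kept, weekly counts | Not excluded if weekly counts are further investigation | No must-record trigger met | Not clearly: laboratory listing names serum chemistry only |
| Grade 4 neutropenia, idelalisib withheld (required) | Not excluded | Must record (interruption) | Not needed |
| Grade 3 ALT/AST/bilirubin, idelalisib withheld (recommended) | Not excluded | Must record (interruption) | Yes, liver listing |
| Grade 3 ALT/AST/bilirubin, asymptomatic, investigator continues dosing, weekly tests (required) | Not excluded if weekly tests are further investigation | No must-record trigger met | Yes, liver listing |

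The last column for the liver rows follows from the thresholds. Table 5-2 puts Grade 3 at ALT/AST above 5 × ULN or bilirubin above 3 × ULN. SAP Section 7.2.2 lists subjects from ALT/AST above 3 × ULN and from bilirubin above 1.5 × ULN, so every Grade 3 value is caught. SAP Section 7.2.1 speaks of grading laboratory results in general, but the SAP describes no hematology or ANC listing.

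**Step 4. Scale.** Assume one subject's only Grade ≥3 AE is the unrecorded event. Incidence changes by 1/N. Exact (Clopper-Pearson) 95% intervals are in brackets; for 0/N the upper limit is 1 − 0.025^(1/N).

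- N = 3 (enrolled, SAP Section 1.3): 0/3 = 0.0% (0 to 70.8%) instead of 1/3 = 33.3% (0.8 to 90.6%).
- N = 6 (planned, Protocol Section 4.1): 0/6 = 0.0% (0 to 45.9%) instead of 1/6 = 16.7% (0.4 to 64.1%).

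If the subject has another recorded Grade ≥3 AE, subject-level incidence does not change and only a line in the listing is lost.

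**The case against.** The strongest reply is that the two sections can be read together. Section 7.1.3 sets a minimum for what must be recorded. It does not say that an abnormality needing further investigation is exempt, and Section 7.4 separately requires every AE to be reported. A careful site could treat any abnormality that prompts protocol-required testing as clinically significant and record it. It can also be argued that weekly counts are only more frequent monitoring, in which case the extra counts alone would not make the event an AE under either section. This stands so far: the sections are ambiguous, not flatly opposed. It does not remove the problem, because the outcome still turns on two terms that the protocol leaves undefined.

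A reader might infer that Grade 3 transaminase elevation sits in the same gap. The documents do not support that as a parallel case. The recommended action is to withhold, Section 7.3.3 describes withholding, and withholding is an interruption that 7.1.3 requires to be recorded. Omission needs a departure from the recommendation, which Section 5.2.10 permits, and the value would still be in the SAP liver listing. It would be lost from the AE endpoint but not from the report.

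A reader might also infer that idelalisib will look safer than it was. Nothing in the documents shows that an event was missed. There is no primary endpoint and no comparator, and the SAP describes AE listings rather than a Grade ≥3 incidence table.

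**Conclusion.** The point holds for asymptomatic Grade 3 neutropenia managed on the protocol's recommended path. It can be recorded as an AE or not by sites that both comply, it then may or may not enter the Grade ≥3 AE endpoint, and the SAP does not clearly show ANC elsewhere. For Grade 3 ALT, AST or bilirubin the effect is confined to cases where dosing continues despite the recommendation, and those values remain visible.

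The conclusion assumes that required weekly counts can reasonably be called further investigation and that the event has no symptoms and no treatment. The size, 0/3 instead of 1/3, further assumes that the subject has no other Grade ≥3 AE; it should not be read as the effect of any one unrecorded event. In practice the loss is a missing line in a 3-subject listing. That is modest but avoidable.

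**What to change.** - **Protocol Sections 7.1.1 and 7.1.3.** Use one laboratory-AE criterion in both. State that a Grade ≥3 laboratory abnormality that triggers protocol-required additional testing is recorded as an AE even if the dose is unchanged. Tie the trigger to Grade ≥3 and not to every required action in Table 5-2: the neutropenia row with weekly counts is printed as Grade ≤ 3, so a broader trigger could draw in Grade 1 and 2 values.
- **Data review.** Before database finalization, query Grade ≥3 ANC, ALT, AST and bilirubin values that have no matching AE record. This remains useful even if the protocol change comes late, since the 3 subjects are already enrolled.
- **SAP Section 7.2.** Add ANC to the laboratory listing.
- **Table 5-2.** Separately, reconcile the printed Grade ≤ 3 neutropenia row label with Section 7.3.4, which ties weekly counts to Grade 3. This is a matter of consistency and changes no dose rule.

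The cost is a few more AE entries and queries, one added listing, and a protocol modification that needs ethics committee approval under Section 9.2.1. If the SAP is already final, SAP Section 1 calls for the change to be documented in the CSR.
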